Myositis or inflammatory myopathies are a group of disorders sharing the common feature of inflammatory muscle injury; dermatomyositis and polymyositis are among the most common disorders. Initial diagnosis is based on clinical (muscle weakness, muscle pain, skin rash in dermatomyositis), biochemical (serum creatine kinase increase), and imaging (electromyography/MRI) features, and is confirmed with a muscle biopsy.

Participants with signs and symptoms of myositis, in the absence of an identified alternate etiology, should be treated according to the guidelines in [Table 13](#).

Table 13 Management Guidelines for Immune-Mediated Myositis

Event	Management
Immune-mediated myositis, Grade 1	
Continue RO7296682 and/or atezolizumab.Refer participant to rheumatologist or neurologist.Initiate treatment as per institutional guidelines.
Immune-mediated myositis, Grade 2	
Withhold RO7296682 and/or atezolizumab after event onset^a and contact the Medical Monitor.Refer participant to rheumatologist or neurologist.Initiate treatment as per institutional guidelines.Consider treatment with corticosteroids equivalent to 1–2 mg/kg/day IV methylprednisolone and convert to 1–2 mg/kg/day oral prednisone or equivalent upon improvement.If corticosteroids are initiated and event does not improve within 48 hours after initiating corticosteroids, consider adding an immunosuppressive agent.If event resolves to Grade 1 or better, resume RO7296682 and/or atezolizumab.^bIf event does not resolve to Grade 1 or better while withholding RO7296682 and/or atezolizumab, permanently discontinue RO7296682 and/or atezolizumab and contact the Medical Monitor.^c

Event	Management
Immune-mediated myositis, Grade 3	
 Withhold RO7296682 and/or atezolizumab after event onset ^a and contact Medical Monitor. Refer participant to rheumatologist or neurologist. Initiate treatment as per institutional guidelines. Respiratory support may be required in more severe cases. Initiate treatment with corticosteroids equivalent to 1–2 mg/kg/day IV methylprednisolone, or higher-dose bolus if patient is severely compromised (e.g., cardiac or respiratory symptoms, dysphagia, or weakness that severely limits mobility); convert to 1–2 mg/kg/day oral prednisone or equivalent upon improvement. If event does not improve within 48 hours after initiating corticosteroids, consider adding an immunosuppressive agent. If event resolves to Grade 1 or better, resume RO7296682 and/or atezolizumab. ^b If event does not resolve to Grade 1 or better while withholding RO7296682 and/or atezolizumab, permanently discontinue RO7296682 and/or atezolizumab and contact Medical Monitor. ^c For recurrent events, treat as a Grade 4 event. Permanently discontinue RO7296682 and/or atezolizumab and contact the Medical Monitor. ^c
Immune-mediated myositis, Grade 4	
 Permanently discontinue RO7296682 and/or atezolizumab and contact the Medical Monitor. ^c Refer participant to rheumatologist or neurologist. Initiate treatment as per institutional guidelines. Respiratory support may be required in more severe cases. Initiate treatment with corticosteroids equivalent to 1–2 mg/kg/day IV methylprednisolone, or higher-dose bolus if patient is severely compromised (e.g., cardiac or respiratory symptoms, dysphagia, or weakness that severely limits mobility); convert to 1–2 mg/kg/day oral prednisone or equivalent upon improvement. If event does not improve within 48 hours after initiating corticosteroids, consider adding an immunosuppressive agent. If event resolves to Grade 1 or better, taper corticosteroids over \geq1 month.

^a RO7296682 and/or atezolizumab may be withheld for a longer period (i.e., >12 weeks after event onset) to allow for corticosteroids (if initiated) to be reduced to the equivalent of ≤ 10 mg/day oral prednisone. The acceptable length of the extended period must be agreed upon by the investigator and the Medical Monitor.

^b If corticosteroids have been initiated, they must be tapered over \geq 1 month to the equivalent of ≤ 10 mg/day oral prednisone before RO7296682 and/or atezolizumab can be resumed.

^c Resumption of RO7296682 and/or may be considered in participants who are deriving benefit and have fully recovered from the immune-mediated event. Participants can be re-challenged with RO7296682 and/or atezolizumab only after approval has been documented by the Investigator (or an appropriate delegate) and the Medical Monitor.

HEMOPHAGOCYTIC LYMPHOHISTIOCYTOSIS AND MACROPHAGE ACTIVATION SYNDROME

Immune-mediated reactions may involve any organ system and may lead to hemophagocytic lymphohistiocytosis (HLH) and macrophage activation syndrome (MAS).

Clinical and laboratory features of severe CRS overlap with HLH, and HLH should be considered when CRS presentation is atypical or prolonged.

Participants with suspected HLH should be diagnosed according to published criteria by [McClain and Eckstein \(2014\)](#). A participant should be classified as having HLH if five of the following eight criteria are met:

- Fever $\geq 38.5^{\circ}\text{C}$.
- Splenomegaly.
- Peripheral blood cytopenia consisting of at least two of the following:
 - Hemoglobin $< 90 \text{ g/L}$ (9 g/dL) ($< 100 \text{ g/L}$ [10 g/dL] for infants < 4 weeks old).
 - Platelet count $< 100 \times 10^9/\text{L}$ ($100,000/\mu\text{L}$).
 - ANC $< 1.0 \times 10^9/\text{L}$ ($1000/\mu\text{L}$).
- Fasting triglycerides $> 2.992 \text{ mmol/L}$ (265 mg/dL) and/or fibrinogen $< 1.5 \text{ g/L}$ (150 mg/dL).
- Hemophagocytosis in bone marrow, spleen, lymph node, or liver.
- Low or absent natural killer cell activity.
- Ferritin $> 500 \text{ mg/L}$ (500 ng/mL).
- Soluble interleukin 2 (IL-2) receptor (soluble CD25) elevated ≥ 2 standard deviations above age-adjusted laboratory-specific norms.

Participants with suspected MAS should be diagnosed according to published criteria for systemic juvenile idiopathic arthritis by [Ravelli et al. \(2016\)](#). A febrile participant should be classified as having MAS if the following criteria are met:

- Ferritin $> 684 \text{ mg/L}$ (684 ng/mL).
- At least two of the following:
 - Platelet count $\leq 181 \times 10^9/\text{L}$ ($181,000/\mu\text{L}$).
 - AST $\geq 48 \text{ U/L}$.
 - Triglycerides $> 1.761 \text{ mmol/L}$ (156 mg/dL).
 - Fibrinogen $\leq 3.6 \text{ g/L}$ (360 mg/dL).

Participants with suspected HLH or MAS should be treated according to the guidelines in [Table 14](#).

Table 14 Management Guidelines for Suspected Hemophagocytic Lymphohistiocytosis or Macrophage Activation Syndrome

Event	Management
Suspected HLH or MAS	
• Permanently discontinue RO7296682 and/or atezolizumab and contact the Medical Monitor.• Consider participant referral to hematologist.• Initiate supportive care, including intensive care monitoring if indicated per institutional guidelines.• Consider initiation of IV corticosteroids, an immunosuppressive agent, and/or anti-cytokine therapy.• If event does not respond to treatment within 24 hours, contact the Medical Monitor and initiate treatment as appropriate according to published guidelines (La Rosée 2015; Schram and Berliner 2015; La Rosée et al. 2019).• If event resolves to Grade 1 or better, taper corticosteroids over ≥ 1 month.

HLH=Hemophagocytic lymphohistiocytosis; MAS=Macrophage activation syndrome.

REFERENCES

La Rosée P. Treatment of hemophagocytic lymphohistiocytosis in adults. *Hematology Am Soc Hematol Educ Protragm*. 2015;1:190-6.

Appendix 13

New Response Evaluation Criteria in Solid Tumors—Version 1.1

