5. REFERENCES

R Core Team. 2017. R: A language and environment for statistical computing. Vienna, Austria: R Foundation for Statistical Computing. Available from: <https://www.R-project.org/>.

Appendix 12

Management Guidelines for imAEs with RO7296682 and/or Combination Therapy with RO7296682 and Atezolizumab

PULMONARY EVENTS

Pulmonary events may present as new or worsening dyspnea, cough, chest pain, fever, dyspnea, fatigue, hypoxia, pneumonitis, and pulmonary infiltrates. Participants will be assessed for pulmonary signs and symptoms throughout the study and will also have CT scans of the chest performed at every tumor assessment.

All pulmonary events should be thoroughly evaluated for other commonly reported etiologies such as pneumonia or other infection, lymphangitic carcinomatosis, pulmonary embolism, heart failure, chronic obstructive pulmonary disease, or pulmonary hypertension. *COVID-19 evaluation should be performed per institutional guidelines where relevant.* Management guidelines for pulmonary events are provided in [Table 1](#).

Table 1 Management Guidelines for Pulmonary Events, Including Pneumonitis

Event	Management
Pulmonary event, Grade 1	
 Continue RO7296682 and/or atezolizumab and monitor closely. Re-evaluate on serial imaging. Consider participant referral to pulmonary specialist.

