Pulmonary event, Grade 2	
 Withhold after event onset.^a Refer participant to pulmonary and infectious disease specialists and consider bronchoscopy or BAL with or without transbronchial biopsy. Initiate treatment with corticosteroids equivalent to 1 to 2 mg/kg/day oral prednisone. If event resolves to Grade 1 or better, resume RO7296682 and/or atezolizumab.^b If event does not resolve to Grade 1 or better while withholding RO7296682 and/or atezolizumab, permanently discontinue RO7296682 and/or atezolizumab and contact Medical Monitor.^{c, d} For recurrent events, treat as a Grade 3 or 4 event.
Pulmonary event, Grade 3 or 4	
 Permanently discontinue RO7296682 and/or atezolizumab and contact the Medical Monitor.^c Oral or IV broad-spectrum antibiotics should be administered in parallel to the immunosuppressive treatment. Bronchoscopy or BAL with or without transbronchial biopsy is recommended. Initiate treatment with corticosteroids equivalent to 1 to 2 mg/kg/day oral prednisone. If event does not improve within 48 hours after initiating corticosteroids, consider adding an immunosuppressive agent. If event resolves to Grade 1 or better, taper corticosteroids over ≥ 1 month.

BAL = Bronchoscopic alveolar lavage.

- ^a RO7296682 and/or atezolizumab may be withheld for a longer period (i.e., >12 weeks after event onset) to allow for corticosteroids (if initiated) to be reduced to the equivalent of ≤ 10 mg/day oral prednisone. The acceptable length of the extended period must be agreed upon by the Investigator and the Medical Monitor.
- ^b If corticosteroids have been initiated, they must be tapered over ≥ 1 month to the equivalent of ≤ 10 mg/day oral prednisone before RO7296682 and/or atezolizumab can be resumed.
- ^c Resumption of RO7296682 and/or atezolizumab may be considered in participants who are deriving benefit and have fully recovered from the immune-mediated event. Participants can be re-challenged with RO7296682 and/or atezolizumab only after approval has been documented by the Investigator (or an appropriate delegate) and the Medical Monitor.
- ^d *In case of pneumonitis, atezolizumab should not be resumed after permanent discontinuation.*

HEPATIC EVENTS

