Renal event, Grade 1	
 Continue RO7296682 and/or atezolizumab. Monitor kidney function, including creatinine, closely until values resolve to within normal limits or to baseline values.
Renal event, Grade 2	
 Withhold RO7296682 and/or atezolizumab for up to 12 weeks after event onset.^a Refer participant to renal specialist. Initiate treatment with corticosteroids equivalent to 1–2 mg/kg/day oral prednisone. If event resolves to Grade 1 or better, resume RO7296682 and/or atezolizumab.^b If event does not resolve to Grade 1 or better while withholding RO7296682 and/or atezolizumab, permanently discontinue RO7296682 and/or atezolizumab and contact the Medical Monitor.^c
Renal event, Grade 3 or 4	
 Permanently discontinue RO7296682 and/or atezolizumab and contact the Medical Monitor. Refer participant to renal specialist and consider renal biopsy. Initiate treatment with corticosteroids equivalent to 1–2 mg/kg/day oral prednisone. If event does not improve within 48 hours after initiating corticosteroids, consider adding an immunosuppressive agent. If event resolves to Grade 1 or better, taper corticosteroids over \geq 1 month.

^a RO7296682 and/or atezolizumab may be withheld for a longer period (i.e., $>$ 12 weeks after event onset) to allow for corticosteroids (if initiated) to be reduced to the equivalent of \leq 10 mg/day oral prednisone. The acceptable length of the extended period must be agreed upon by the Investigator and the Medical Monitor.

^b If corticosteroids have been initiated, they must be tapered over \geq 1 month to the equivalent of \leq 10 mg/day oral prednisone before RO7296682 and/or atezolizumab can be resumed.

^c Resumption of RO7296682 and/or atezolizumab may be considered in participants who are deriving benefit and have fully recovered from the immune-mediated event. Participants can be re-challenged with RO7296682 and/or atezolizumab only after approval has been documented by the Investigator (or an appropriate delegate) and the Medical Monitor.

IMMUNE-MEDIATED MYOSITIS

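### Appendix 12, Table 1 marks the bar on resuming atezolizumab after pneumonitis on the Grade 2 row but not on the Grade 3 or 4 row

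*Combined protocol and SAP*

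**What the plan says.** Appendix 12, Table 1 is titled "Management Guidelines for Pulmonary Events, Including Pneumonitis", so it covers pneumonitis and other pulmonary events. Two of its rows order permanent discontinuation.

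- **Grade 2.** If the event does not resolve to Grade 1 or better while drug is withheld, the instruction is "permanently discontinue RO7296682 and/or atezolizumab and contact Medical Monitor.^{c, d"; the superscript is c and d. The row also says of repeat episodes: "For recurrent events, treat as a Grade 3 or 4 event".
- **Grade 3 or 4.** The instruction is "Permanently discontinue RO7296682 and/or atezolizumab and contact the Medical Monitor.^c"; the superscript is c alone.

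The two footnotes say different things.

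- **Footnote c:** "Resumption of RO7296682 and/or atezolizumab may be considered in participants who are deriving benefit and have fully recovered from the immune-mediated event". Re-challenge may happen "only after approval has been documented by the Investigator (or an appropriate delegate) and the Medical Monitor".
- **Footnote d:** "In case of pneumonitis, atezolizumab should not be resumed after permanent discontinuation". It is printed in italics, which the Version 4 amendment rationale uses for substantial new information. That rationale lists the pulmonary guidelines of Appendix 12 among those updated.

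**The concern.** A footnote is normally taken to apply where its marker stands. On that reading, atezolizumab may not be restarted after a Grade 2 pneumonitis that failed to resolve, but restarting it stays open to discretion after a Grade 3, Grade 4 or recurrent pneumonitis. The stricter rule is attached to the milder event, and the documents give no reason for that ordering.

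This is an operative safety rule. A site that follows the marker on the Grade 3 or 4 row is directed to the re-challenge option and not to the pneumonitis bar. Section 8.3.9 describes the trial as the first human evaluation of this combination, with the actual risk of combined toxicity unknown. Section 8.3.6 lists pneumonitis among the atezolizumab events that must be reported to the sponsor immediately. The re-challenge rule for the severe grades should therefore be unambiguous.

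**Working it through.** No arithmetic beyond counting markers applies. The markers below are as read from the PDF text.

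**Step 1. Rows of Table 1 side by side.**

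| Row | Orders permanent discontinuation? | Marked c | Marked d |
|---|---|---|---|
| Grade 1 | No | – | – |
| Grade 2, unresolved | Yes | Yes | Yes |
| Grade 3 or 4, and recurrent Grade 2 by referral | Yes | Yes | No |

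Of the 2 rows that order permanent discontinuation, c is marked on 2 and d on 1.

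**Step 2. What each marker does.** Footnote c leaves re-challenge with either drug to a case-by-case decision by the Investigator and the Medical Monitor. Footnote d removes that choice for atezolizumab after pneumonitis. A row marked c only, read by its marker, keeps the choice open.

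**Step 3. Does any other text apply the bar to the Grade 3 or 4 row?** None was found. Section 8.3.9.3 has a general statement that atezolizumab may be resumed, without a pneumonitis exception. That section is limited to events not specifically listed in Appendix 12, so it neither closes nor widens the gap. Footnote d is the only bar, which is why its placement matters.

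**Step 4. Do markers differ by row elsewhere in the appendix?** Table 12 (renal events) also has 2 rows that order permanent discontinuation. It defines footnote c, marks it on the Grade 2 row and leaves it off the Grade 3 or 4 row, a count of 1 of 2. A reader could take row-level markers there as carrying the rule. Whether that omission was intended is unknown, so this is weak support and the conclusion does not depend on it.

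**Step 5. Should d replace c on the Grade 3 or 4 row?** No. The table covers pulmonary events other than pneumonitis, and d does not mention RO7296682. Footnote c still has a use on that row, so the row needs both markers.

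**The case against.** The strongest reply is that the rule is already stated for every grade. Footnote d names no grade, and the Grade 3 or 4 row orders permanent discontinuation, so d covers that row by its own words. On this view c is the general permission, d is the specific exception, and nothing conflicts. The path to harm is also thin: a site sent to c finds d on the next line, the bullet itself requires contact with the Medical Monitor, and c requires full recovery and documented approval. Finally, the point rests on one superscript letter in text extracted from a PDF, and the extracted text has words missing elsewhere in this appendix.

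Much of this stands. The defect is a missing marker and not a statement permitting re-challenge, and the approval step is a real safeguard. A superscript lost in extraction cannot be excluded, although it is less likely because c was captured on the Grade 3 or 4 bullet and both letters were captured on the Grade 2 bullet of the same table.

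The reply does not explain why d is marked on one row at all. If d is meant for all grades, adding the marker only states that intent. If it is meant for Grade 2 alone, the documents offer no rationale.

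**Conclusion.** The concern holds as a minor internal inconsistency in a safety rule. As marked, Table 1 bars atezolizumab after unresolved Grade 2 pneumonitis and points to possible re-challenge after Grade 3, Grade 4 or recurrent pneumonitis. How many participants this could affect cannot be estimated, because the documents give no frequency of pneumonitis in this trial. The practical risk is limited by the wording and position of footnote d and by the required approval. Nothing in the efficacy analyses, sample size or error rates changes. The conclusion assumes that the superscripts were read correctly from the PDF.

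**What to change.** In Appendix 12, Table 1, mark the permanent-discontinuation bullet of the Grade 3 or 4 row with both c and d, and begin footnote c with *Subject to footnote d*. The marker places the bar on the row where it is missing. The added words settle which footnote prevails and keep c available for other pulmonary events and for RO7296682.

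The cost is one footnote marker and four words at the next amendment, with none to participants or to the design.

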1. MEASURABILITY OF TUMOR AT BASELINE

1.1 **DEFINITIONS**

At baseline, tumor lesions/lymph nodes will be categorized measurable or non-measurable as follows:

1.1.1 Measurable Tumor Lesions

Tumor lesions must be accurately measured in at least one dimension (longest diameter in the plane of measurement is to be recorded) with a minimum size of:

- 10 mm by computed tomography (CT) or magnetic resonance imaging (MRI) scan (CT/MRI scan slice thickness/interval no greater than 5 mm).
- 10 mm caliper measurement by clinical exam (lesions, which cannot be accurately measured with calipers should be recorded as non-measurable).
- 20 mm by chest x-ray.

Malignant lymph nodes: To be considered pathologically enlarged and measurable, a lymph node must be ≥ 15 mm in short axis when assessed by CT scan (CT scan slice thickness recommended to be not greater than 5 mm). At baseline and in follow-up, only the short axis will be measured and followed. See also Section 2.2 on “Baseline documentation of target and non-target lesions” for information on lymph node measurement.

1.1.2 Non-measurable Tumor Lesions

Non-measurable tumor lesions encompass small lesions (longest diameter < 10 mm or pathological lymph nodes with ≥ 10 to < 15 mm short axis) as well as truly non-measurable lesions. Lesions considered truly non-measurable include leptomeningeal disease, ascites, pleural or pericardial effusion, inflammatory breast disease, lymphangitic involvement of skin or lung, peritoneal spread, and abdominal masses/abdominal organomegaly identified by physical exam that are not measurable by reproducible imaging techniques.

1.1.3 Special Considerations Regarding Lesion Measurability

Bone lesions, cystic lesions, and lesions previously treated with local therapy require particular comment:

Bone lesions:

- Bone scan, positron emission tomography scan, or plain films are not considered adequate imaging techniques to measure bone lesions. However, these techniques can be used to confirm the presence or disappearance of bone lesions.
- Lytic bone lesions or mixed lytic-blastic lesions, with identifiable soft tissue components, that can be evaluated by cross-sectional imaging techniques such as CT or MRI can be considered as measurable lesions if the soft tissue component meets the definition of measurability described above.
- Blastic bone lesions are non-measurable.

Cystic lesions:

- Lesions that meet the criteria for radiographically defined simple cysts should not be considered as malignant lesions (neither measurable nor non-measurable) because they are, by definition, simple cysts.
- “Cystic lesions” thought to represent cystic metastases, can be considered as measurable lesions if they meet the definition of measurability described above. However, if non-cystic lesions are present in the same participant, these are preferred for selection as target lesions.

Lesions with previous local treatment:

- Tumor lesions situated in a previously irradiated area, or in an area subjected to other loco-regional therapy, are usually not considered measurable unless there has been demonstrated progression in the lesion.

1.2 TARGET LESIONS: SPECIFICATIONS BY METHODS OF MEASUREMENTS

1.2.1 Measurement of Lesions

All measurements should be recorded in metric notation, using calipers if clinically assessed. All baseline evaluations should be performed as close as possible to the treatment start and never more than 4 weeks before the beginning of the treatment.

1.2.2 Method of Assessment

The same method of assessment and the same technique should be used to characterize each identified and reported lesion at baseline and during study. Imaging based evaluation should always be the preferred option.

Clinical lesions: Clinical lesions will only be considered measurable when they are superficial and ≥ 10 mm diameter as assessed using calipers (e.g., skin nodules). For the case of skin lesions, documentation by color photography including a ruler to estimate the size of the lesion is suggested.

Chest x-ray: Chest CT is preferred over chest x-ray, particularly when progression is an important endpoint, because CT is more sensitive than x-ray, particularly in identifying new lesions. However, lesions on chest x-ray may be considered measurable if they are clearly defined and surrounded by aerated lung.

CT, MRI: CT is the best currently available and reproducible method to measure lesions selected for response assessment. This guideline has defined measurability of lesions on CT scan based on the assumption that CT slice thickness is 5 mm or less. When CT scans have slice thickness greater than 5 mm, the minimum size for a measurable lesion should be twice the slice thickness. MRI is also acceptable.

If before enrollment, it is known that a participant is unable to undergo CT scans with intravenous contrast because of allergy or renal insufficiency, the decision as to whether a non-contrast CT or MRI (without intravenous contrast) will be used to evaluate the participant at baseline and during study, should be guided by the tumor type under investigation and the anatomic location of the disease. For participants who develop contraindications to contrast after baseline contrast CT is done, the decision as to whether non-contrast CT or MRI (enhanced or non-enhanced) will be performed, should also be based on the tumor type, anatomic location of the disease and should be optimized to allow for comparison to the previous studies if possible. Each case should be discussed with the radiologist to determine if a substitution of these other approaches is possible and, if not, the participant should be considered not evaluable from that point forward.

Ultrasound: Ultrasound is not useful in assessment of lesion size and should not be used as a method of measurement.

